2.3.2 Benefit Assessment

Benefits of benralizumab include clinically and statistically significant reductions in annual exacerbation rate, improved lung function, and improved symptom control. These would in turn result in better health-related quality of life and lower systemic steroid exposure. Participants in this study will also contribute to furthering the understanding of the short-term benefits of sustained depletion of airway eosinophils by benralizumab on airway dynamics and mucus plugs in severe eosinophilic asthma.

2.3.3 Overall Benefit: Risk Conclusion

Taking into account the measures taken to minimize risk to participants participating in this study, the potential risks identified in association with benralizumab are justified by the anticipated benefits that may be afforded to participants with severe asthma and with an eosinophilic phenotype.

3 OBJECTIVES AND OUTCOME MEASURES

Table 2 Objectives and Outcome Measures

See footnote for abbreviations mentioned on the table below.

Obj	jectives	Outcome measures ^a							
Prir	nary								
dyn ben airv	describe the change from baseline in airway amics after 13 weeks following treatment with ralizumab, using total mucus volume (specific way volume) measurements from untrimmed ways.	Unadjusted mean within subject difference in total mucus volume measured at TLC, calculated as the mean change from baseline (week 0) at week 13 (\pm 5 days).							
Sec	ondary								
1.	To describe the change from baseline in airway dynamics at week 13 following treatment with benralizumab, as measured by secondary FRI endpoints ^b , irrespective of patient characteristics.	Unadjusted mean within subject difference in secondary FRI endpoints (total mucus plugs score at TLC; total air trapping at FRC; trimmed distal iVaww at TLC; trimmed distal siVaw at TLC and FRC; total iVlung at TLC and FRC), comparing baseline (week 0) to week 13 (± 5 days).							
2.	To describe the relationship between airway dynamics and conventional lung function measurements, cross-sectionally (at week 0) and irrespective of patient characteristics.	Correlation between imaging endpoints (primary and secondary FRI endpoints ^b) and pre-bronchodilator forced expiratory volume in 1 second (pre-BD FEV ₁) at week 0. Correlation between imaging endpoints (primary and secondary FRI endpoints ^b) and pre-bronchodilator forced vital capacity (pre-BD FVC) at week 0. Scatter plots of primary and secondary FRI endpoints ^b and mucus plugs score versus conventional lung function measures (pre-BD FEV ₁ and pre-BD FVC) at week 0. Estimated increases in primary and secondary FRI endpoints ^b and mucus plugs score for every one percent increase in pre-BD FEV ₁ and pre-BD FVC at week 0.							
3.	To describe the relationship between changes from baseline (week 0) in airway dynamics and conventional lung function measurements at week 13, after accounting for baseline measurements of conventional lung function.	Correlation between the change from week 0 in imaging endpoints (primary and secondary FRI endpoints ^b) at week 13 and the change from week 0 in pre-BD FEV ₁ at week 13 (\pm 5 days), overall and within subgroups conditional on the baseline value of pre-BD FEV ₁ . Correlation between the change from week 0 in imaging endpoints (primary and secondary FRI endpoints ^b) at week 13 and the change from week 0 in pre-BD FVC at week 13 (\pm 5 days), overall and within subgroups conditional on the baseline value of pre-BD FVC at week 13 (\pm 5 days), overall and within subgroups conditional on the baseline value of pre-BD FVC.							

	Scatter plots of changes from week 0 in primary and secondary FRI endpoints ^b and mucus plugs score at week 13 vs. changes from week 0 in conventional lung function measures (pre-BD FEV ₁ and pre-BD FVC) at week 13. Estimated change over time (week 13 vs. week 0) in primary and secondary FRI endpoints ^{ab} , with and without adjustment for conventional lung function measures (pre-BD FEV ₁ and pre-BD FVC).
Safety	
To monitor the safety and tolerability of benralizumab.	 Safety and tolerability will be evaluated in terms of AEs, Vital signs, and Clinical laboratory. Assessments related to AEs include: Occurrence/Frequency Relationship to IP or study procedure as
	assessed by investigator
	– Intensity
	- Seriousness
	– Death
	 AEs leading to discontinuation of IP
	 Other significant AEs
	 Time to onset
	Vital signs parameters include systolic and diastolic blood pressure, and heart rate.
/ CCI	
CCI	

- a. FRI endpoints are untrimmed unless otherwise specified (Section 8.1.1.1).
- b. The primary FRI endpoint is total mucus volume at TLC; secondary FRI endpoints for evaluation under secondary objectives include total mucus plugs score at TLC, total air trapping at FRC; trimmed distal iVaww at TLC; trimmed distal siVaw at TLC and FRC; total iVlung at TLC and FRC; and total mucus plugs score at TLC.

CCI	; AE =
adverse event; CCI	; $FEV_1 = Forced$ expiratory volume in 1 second; $FRC = Functional$
residual capacity; FRI = Funct	onal Respiratory Imaging; FVC = Forced vital capacity; IP =
investigational product; iVaw	= Airway wall volume, iVlung = Lung volume, CCl
CCI ;CCI	; (CC)
siVaw = Specific airway volu	e; TLC = Total Lung Capacity.

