9.4.2.2 Secondary Objectives

For the secondary objective 1, univariate paired *t*-tests and mixed effects modelling will be used to assess whether there are statistically significant differences in the means of secondary FRI endpoints (untrimmed total mucus plugs score at TLC, untrimmed total air trapping at FRC, trimmed distal iVaww at TLC, trimmed distal siVaw at TLC and FRC, and untrimmed total iVlung at TLC and FRC) at week 0 vs week 13, unadjusted for patient characteristics.

Secondary analysis of each secondary endpoint will be a mixed-effects model to incorporate the repeated measurements (corresponding to the different lobes) for each subject. The model will estimate the average change from baseline in secondary endpoint at week 0 vs week 13 per lobe, after accounting for the baseline measurement of the secondary endpoint per lobe and heterogeneity across lobes.

For secondary objective 2, a scatter plot will be used to display values of imaging endpoints (primary and secondary FRI parameters) and conventional lung function measures (pre-BD FEV₁ and pre-BD FVC response) at week 0, to get a first indication of the relationship between endpoints at baseline. Spearman's rank correlation coefficients will describe the strength of the association between two endpoints. Pearson correlation will also be used for linear relationships. Regression models will be used to estimate the average increase in imaging endpoints per unit increase in conventional lung function measures, with 95% confidence intervals.

For secondary objective 3, a scatter plot will be used to display changes from baseline at

week 13 in imagine endpoints (primary and secondary FRI parameters) against changes from baseline at week 13 in conventional lung function measures (pre-BD FEV₁ and pre-BD FVC response). Both Spearman's rank and Pearson correlation coefficients will describe the strength of the association. If changes from baseline in conventional lung function measures at week 13 are related to baseline values, as indicated by fitted regression models, correlation coefficients will be reported per subgroup defined by baseline value.

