A linear regression model for imaging endpoints will be fitted, consisting of a binary explanatory variable (corresponding to week 13). The regression coefficient for time will estimate the change from baseline (week 13 vs week 0) in the imaging endpoint. The model will be fitted with and without the inclusion of the change from baseline in pre-BD FEV₁ and pre-BD FVC as individual covariates. Estimated regression coefficients for time from the unadjusted and adjusted models will be compared, to indicate whether the change from baseline in the imaging parameter is explained by changes in pre-BD FEV₁ and pre-BD FVC. Estimated regression coefficients for changes in pre-BD FVC will be reported, to quantify the average change in each imaging endpoint for every one percent increase in pre-BD FEV₁ and pre-BD FVC.

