3.2.4.3 Handling of Dropouts and Missing Data

The populations of interest do not include participants withdrawing before Week 13 and participants with one of the two measurements missing and so will not be included in the analysis.

3.2.4.4 Primary Analysis of Secondary Endpoint 3

For secondary objective 3, a scatter plot will be used to display changes from baseline at Week 13 in each imaging endpoint (including: all FRI endpoints in Table 2) against changes from baseline at Week 13 in each conventional lung function measure (including: pre-BD FEV₁ and pre-BD FVC). Both Spearman's rank and Pearson correlation coefficients will be used to describe the strength of the association between changes from baseline at Week 13 in each imaging endpoint and both of the conventional lung function measures. Estimated correlation coefficients will be reported with corresponding 95% CIs and p-values, testing the null hypothesis of no correlation.

Changes from baseline in conventional lung function measures at Week 13 may be related to baseline values. Therefore, correlation coefficients between each imaging parameter and conventional lung function measure will be reported for the overall populations and for two subgroups, based on dichotomizing at the median baseline value.

To estimate the average change from baseline (Week 13 versus Week 0) in each imaging endpoint, a linear regression model for the change from baseline in each imaging endpoint will be fitted, with adjustment for the baseline (Week 0) measurement of the imaging endpoint. The model will be fitted with and without the inclusion of the change from baseline in pre-BD FEV₁ and pre-BD FVC as individual covariates. Models including and excluding conventional lung function measures as covariates are defined below and are referred to as adjusted and unadjusted models, respectively.

The adjusted linear regression model will be as follows:

$$y_i = \beta_0 + \beta_1 x_{1i} + \beta_2 x_{2i}$$

Where:

• y_i is the change from baseline at Week 13 in the imaging endpoint
- β_0 quantifies the average change from baseline at Week 13 in the imaging endpoint after accounting for the baseline value
- x_{li} is the baseline value at Week 0 of the imaging endpoint
- β₁ quantifies the association between Y and x₁
- x_{2i} is the change from baseline at Week 13 in the conventional lung function measure
- β₂ quantifies the association between Y and x₂, after accounting for baseline measurements

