2.7 Linear Regression Model

In SAP sections 3.2.4 and 3.2.6, it states that more than just the intercept should be displayed in the final outputs however it is the intercept which is of interest and should be reported.

Linear regression models that have a population n < 10 will not be shown in the final outputs.

Throughout the linear regression sections of the SAP there is certain wording that requires more clarity. So, the following sections outline the number of model that should be used for each endpoint.

2.7.1 Secondary Endpoint 3 - Relationship Between Changes from Baseline in Airway Dynamics and Lung Functions Measurements at Week 13

The use of the word unadjusted in the SAP causes confusion over the number of models. Instead, the number of models is outlined explicitly. Three linear models will be fitted for each imaging parameter, where the endpoint will be change from baseline to week 13 in the imaging parameter:

- Model 1: Adjustment for baseline measurement of imaging parameter only
- Model 2: Adjustment for baseline measurement of imaging parameter and for change from baseline to week 13 in pre-BD FEV1
- Model 3: Adjustment for baseline measurement of imaging parameter and for change from baseline to week 13 in pre-BD FVC

CONFIDENTIAL

Developed from TP-BPM-WW-032; related to SOP-BPM-WW-001 D3250R00107

Statistical Analysis Plan Addendum

Table 4outlines the models that are expected for the analysis of tertiary endpoint 1.

Should there be no data for the assigned reference category then the most abundant category will be assigned as the reference.

Table 5 outlines all the of models expected for tertiary endpoint 2

Project Document Version No.: 3.0; Document Effective Date: 03 Sep 24 TP-GDO-WW-169-01 Effective Date: 22 Dec 21 Related to: SOP-GDO-WW-019 CONFIDENTIAL

Developed from TP-BPM-WW-032; related to SOP-BPM-WW-001 D3250R00107

Statistical Analysis Plan Addendum

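### Secondary objective 3 accounts for baseline FEV₁ or FVC only through a median split; a partial correlation in all participants would do so directly and more precisely

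*Protocol*

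**What the plan says.** Objective 3 in Protocol Section 3 (Table 2) concerns the two changes "after accounting for baseline measurements of conventional lung function". The same row lists the correlations as outcome measures, for FVC "overall and within subgroups conditional on the baseline value of pre-BD FVC" and likewise for FEV₁. Protocol 9.4.2.2 makes the subgroup step conditional: if regression shows that lung-function change depends on its baseline, "correlation coefficients will be reported per subgroup defined by baseline value". It gives no cut-point.

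SAP 3.2.4.4 recognises the dependence: "Changes from baseline in conventional lung function measures at Week 13 may be related to baseline values". It then reports correlations overall and in two subgroups, "based on dichotomizing at the median baseline value". Its regressions of imaging change are fitted "with adjustment for the baseline (Week 0) measurement of the imaging endpoint", with or without the change in FEV₁ or FVC.

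SAP Addendum 2.7.1 restates these as three models. Model 1 has baseline imaging only. Model 2 is described as "Adjustment for baseline measurement of imaging parameter and for change from baseline to week 13 in pre-BD FEV1". Model 3 is the same with FVC. Addendum 2.7 says that the intercept is the quantity to report, whereas SAP 3.2.4.4 had also promised the coefficient for lung-function change.

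**The concern.** The objective names baseline lung function as the thing to account for, and the SAP explains why it matters. Yet no regression contains it and no partial correlation is planned. SAP 3.2.4.4 describes the lung-function-change coefficient as holding once baseline measurements are accounted for, but the only baseline measurement in that model is the imaging value. A reader could take it for the adjustment the objective describes.

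The result carries some weight. Protocol 4.2 says that positive correlations between lung-function changes and the primary-endpoint change would support the clinical meaning of the findings. Entry requires pre-BD FEV₁ below 80% of predicted, and there is no control arm, so regression to the mean may contribute to FEV₁ change. If baseline severity also relates to imaging change, the two changes can correlate with no direct link between them.

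**Working it through.** **Where baseline FEV₁ or FVC enters**

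| Place | Analysis | Baseline lung function |
|---|---|---|
| Protocol 9.4.2.2 | Correlations | Subgroups, if dependence is found |
| Protocol 9.4.2.2 | Regression on a week-13 indicator, with or without lung-function change | Absent |
| SAP 3.2.4.4 | Correlations, overall | Absent |
| SAP 3.2.4.4 | Correlations, two halves | Median split |
| SAP 3.2.4.4 and Addendum 2.7.1 | Regressions (Models 1 to 3) | Absent |

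**Inputs.** The planned primary analysis population is 29 (Protocol synopsis), so the halves are 29/2 = 14.5, that is 14 and 15. Tests are two-sided at 5% (Protocol 9.4.1). The 29 was set for the primary endpoint. Its effect size, SD and power are not in the public text, so it cannot be reproduced, and no size calculation for objective 3 is visible. The confounding strengths below are assumptions.

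**Precision.** Fisher's z = atanh(r), with SE = 1/√(n − 3 − k) for k covariates. This applies to Pearson correlations and is approximate for Spearman. For r = 0.3, z = 0.310.

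- n = 14: SE = 1/√11 = 0.302; 0.310 ± 0.591; r from −0.27 to 0.72.
- n = 15: SE = 1/√12 = 0.289; 0.310 ± 0.566; r from −0.25 to 0.70.
- n = 29, unadjusted: SE = 1/√26 = 0.196; 0.310 ± 0.384; r from −0.07 to 0.60.
- n = 29, one covariate: SE = 1/√25 = 0.200; 0.310 ± 0.392; r from −0.08 to 0.61.

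For a true r of 0.5, power is Φ(0.549/SE − 1.96): 45% (n = 14), 48% (n = 15), 80% (all 29, unadjusted) and 78% (all 29, partial). The smallest |r| reaching p < 0.05 is 0.53, 0.51, 0.37 and 0.37.

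**Bias in the correlations.** Suppose normally distributed baseline lung function correlates g in absolute value with each change, and nothing else links the changes. The spurious overall |r| is g². A median split leaves 1 − 2/π = 0.363 of the baseline variance inside each half, so the within-half |r| is 0.363g²/(0.363g² + 1 − g²).

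| g | Overall | Within half | Share left |
|---|---|---|---|
| 0.3 | 0.09 | 0.0327/0.9427 = 0.035 | 39% |
| 0.4 | 0.16 | 0.0581/0.8981 = 0.065 | 40% |
| 0.5 | 0.25 | 0.0908/0.8408 = 0.108 | 43% |

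The partial correlation averages 0 throughout. In simulation (20,000 trials of 29), the overall correlation reached p < 0.05 in about 7.5%, 13% and 26% of trials. Within a half the rate was 5.4% at g = 0.3 and 5.5% at g = 0.4.

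**Bias in Model 2.** Take baseline imaging to correlate ρ = 0.5 in absolute value with baseline FEV₁ (also assumed). The spurious slope on FEV₁ change, in SD units and absolute value, is g²(1 − ρ²)/(1 − g²ρ²).

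- g = 0.3: 0.0675/0.9775 = 0.07.
- g = 0.5: 0.1875/0.9375 = 0.20.

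Simulated false-positive rates for that slope at n = 29 are 6% and 17%, against about 5% once baseline FEV₁ is added. In this scenario, adjusting for baseline imaging absorbs only part of the effect.

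**The case against.** The strongest reply is that the plan does what Table 2 defines. Subgroups by baseline lung function are the listed outcome measure and the SAP supplies the cut-point. The regressions serve another outcome measure in that row, the change over time with and without lung-function adjustment. The objective is descriptive and the SAP plans no multiplicity control. This stands: a reader might infer that objective 3 goes unanswered, and the documents do not support that. The gap is between the objective's wording and how fully the chosen analyses deliver it.

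Three other stronger readings also fail.

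- A reader might infer that only half the data are used at a time. That is true only of the subgroup correlations.
- A reader might infer that every model adjusts for baseline imaging alone. Models 2 and 3 also contain the change in FEV₁ or FVC.
- A reader might infer that confounding is established. The documents give no correlation between baseline lung function and either change. At g = 0.3 and 0.4, false positives within halves stay close to 5%, so the split removes most of the inflation in error rate and loses precision instead.

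A further objection concerns the remedy. SAP 3.2.4.4 compares intercepts between models to judge whether lung-function change explains imaging change. Adding baseline FEV₁ to Model 2 alone would make the two models differ by two covariates, and an uncentred value would place the intercept at an FEV₁ of zero. This is correct, and the fix allows for it.

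**Conclusion.** The point holds in a limited form. Baseline lung function is handled only by a median split, and no model or partial correlation includes it. Under assumed strengths of 0.3 to 0.5, the unadjusted overall correlation is off by about 0.09 to 0.25, and roughly 40% of that survives within halves; weaker links would make it smaller. The firmer cost is precision: the intervals in each half are much wider than those available from an adjusted estimate in everyone. The sample figures rest on the planned 29. The actual number may differ, because the Addendum widens the evaluable set and removes the Visit 4 window. This is a modest issue, worth correcting because the correction is cheap.

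**What to change.** 1. Report partial Pearson and Spearman correlations between imaging change and FEV₁ (or FVC) change, adjusted for the matching baseline value as a continuous variable, in the whole primary analysis population. Keep the median-split correlations as descriptive.
2. Add mean-centred baseline FEV₁ to Model 2 and mean-centred baseline FVC to Model 3. Fit a matching version of Model 1 with each, so that the intercept comparison still isolates change in lung function.
3. Report the lung-function-change coefficient with its interval, as SAP 3.2.4.4 promised, beside the intercept that Addendum 2.7 asks for. The intercept alone does not describe the relationship.

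Spirometry is already collected at Visit 1. The cost is one degree of freedom (power 80% to 78% at r = 0.5) and a few extra outputs, including two added versions of Model 1 per imaging parameter.

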4 STUDY DESIGN

4.1 Overall Design

This is an interventional single group, open-label, uncontrolled, prospective, multicenter clinical trial.

The study will be conducted in male and female participants ≥ 18 years old with established severe eosinophilic asthma, as defined by ERS/ATS clinical guidelines (Chung et al., 2014), inadequately controlled by treatment with ICS-LABA with or without oral corticosteroids (OCS) or other asthma controller medications.

There will be no study intervention assignment applied as this is a single group study.

Each participant will participate in the study for a minimum of 15 weeks and up to 23 weeks from the time when informed consent is obtained through to end of study, inclusive of study follow-up. The following are the sequence and duration of study periods:

- Informed consent and instructions for withholding maintenance and rescue asthma medications for screening (24 hours to 30 days prior to screening)
- Screening visit (V0)
- Visit 1 (V1; week 0; within 1 to 21 days of screening)
- Visit 2 (V2; week 4 ± 5 days)
- Visit 3 (V3; week 8 ± 5 days)
- Visit 4 (V4; week 13 ± 5 days)
- Follow-up (2 weeks [± 7 days] after V4) Phone call follow-up

Refer to Table 1 for further information on the Schedule of Activities (SoA) to be performed throughout the study.

Patients will be discharged from the study after the phone call follow-up is completed. This study will not be extended and there will be no roll-over studies. Refer to Section 6.7 for further information on intervention after the end of the study.

4.2 Scientific Rationale for Study Design

Single-arm design

The decision to conduct a single-arm study instead of a placebo-controlled study was based on several factors.

Firstly, benralizumab has been approved in all major markets, and its efficacy is established in the target patient population. While it is of scientific value to add a placebo arm to this study, this addition in the context of a phase IV study in a population prone to exacerbations, and

with the availability of other biologics for asthma, will complicate study enrolment and increase the number of patients enrolled on both arms, thus delaying the availability of important results from this study. Furthermore, having a placebo arm would be unnecessarily exposing patients to radiation through the study procedure.

Next, as previously discussed, it is noteworthy that FRI endpoints, unlike those derived from spirometry are not influenced by patient effort or muscle force, and are thus less likely to change due to a non-disease-related placebo effect. Several studies in asthma and COPD have demonstrated very low variability in FRI parameters when patients are not subjected to an intervention or when imaged after equivalent maintenance medication withhold periods (De Backer et al., 2012a; De Backer et al., 2016; De Backer et al., 2018; Langton et al., 2019).

A study in an asthmatic population showed no change in airway volumes (siVaw) in repeated high resolution CT scans after 3 to 7 days when equivalent wash-out periods were observed (De Backer et al., 2016). Another study of patients with severe asthma who underwent bronchial thermoplasty also demonstrated that airways in the untreated lung did not change significantly after 4 weeks (Langton et al., 2019). Subsequent variability analysis was undertaken on untreated subjects from a previous double-blind placebo-controlled study on the longitudinal change in FRI endpoints to inform expectations for endpoint progression in untreated patients (data on file). FRI endpoints were measured at weeks 0 and 12 among 22 placebo subjects selected based on similar characteristics to that in the current study (sputum eosinophilia and persistent, moderate-to-severe asthma). In the placebo group, siVaw changed (decreased) an average of -3.46% between weeks 0 and 12, with a 95% CI of (-7.50%, 0.584%), suggesting that subjects not receiving treatment are likely to exhibit stable or declining endpoint values. It should be noted that measures will also be taken during the CT image acquisition process to ensure variability is reduced during this procedure. This includes, but is not limited to, the use of phantom scans to ensure every site adheres to specific scanning protocols provided to them. These quality assurance measures will further improve the signalto-noise ratio.

Apart from the above, previous studies have reported a worsening in airway endpoints in patients treated with placebo. This was observed in a placebo-controlled cross-over study assessing the effect of budesonide/formoterol in patients with COPD (De Backer et al., 2012a), as well as in another placebo-controlled cross-over study assessing the effect of glycopyrrolate/formoterol fumarate in patients with COPD (De Backer et al., 2018). Therefore, the proposal to study within-patient changes from baseline in a single-arm study may perhaps be a more conservative approach compared with a placebo-controlled study design.

Taking the above rationales into consideration, the proposal of a single-arm study design may be the most appropriate approach to meet the study aims and intention. Placebo data in

AstraZeneca

patients with severe asthma will become available from other studies of biologics in severe asthma (NCT04400318) and could be used as a placebo group in future post-hoc analysis.

Correlation analysis conducted by De Backer and colleagues on both patients with asthma (n = 79) and those with COPD (n = 49) suggest that the effect size of FRI outcomes in response to respiratory treatment in asthma and COPD appear to be three-to-four times larger than those in FEV₁, the current gold standard efficacy endpoint (De Backer et al., 2015). The investigators concluded that FRI may be a good tool for evaluating the potentially subtle changes in lung function caused by anti-inflammatory compounds (De Backer et al., 2015). FRI studies in patients with severe asthma following treatment with other biologics are ongoing and data are not available presently.

CT-based mucus plug scoring has been shown to be positively associated with asthma linked eosinophilia (Dunican et al., 2018). Moreover, in patients with asthma, the presence of mucus plugs in four or more lung segments occurred in 67% of patients with FEV₁ (percent predicted) of less than 60%, 19% of patients with FEV₁ from 60%-80%, and 6% of patients with FEV₁ greater than 80% (Dunican et al., 2018). These results suggest that airway occlusion by mucus is plausibly a mechanism underlying airflow obstruction in eosinophilic asthma. Therefore, it could be speculated that benralizumab-mediated eosinophil depletion in severe eosinophilic asthmatics may reduce mucus burden and correspondingly, the degree of airway obstruction.

Current methods for mucus plug scoring are discrete counts that disregard mucus plug size. However, a novel method has been developed as part of FRI that extends mucus plug scoring by measuring the volume of mucus plugs in the airways visible via CT imaging, thereby accounting for variations in mucus plug size through this assessment. Given the established relationship between mucus plugs and airway obstruction, it is also plausible that reduced mucus volume will result in reduced air trapping and increased airway volume as assessed via FRI. These changes may lead to improvements in the participant's lung function and patientreported outcomes (PROs), ultimately allowing the participant to breathe more easily and thus feel better and experience a better quality of life. A clinically meaningful change in the primary endpoint would be a significant change in total untrimmed mucus volume at week 13 from baseline after treatment with benralizumab. Significant changes in FEV₁, forced vital capacity (FVC) and scores from CCI , and positive correlations between these changes and the changes in the primary endpoint would further reflect and support the clinically meaningful improvements in outcomes under benralizumab. It will also allow the results from the current study to be put into context with previous or future findings from studies on benralizumab treatment (see below for further details regarding PROs conducted in previous studies on benralizumab treatment).

Study duration

The primary aim of this study is to understand the short-term impact of benralizumab on airway dynamics and structure that would reflect as improvements in lung function and PRO measurements, that of which were well established in previous trials studying the effects of benralizumab treatment. These improvements in lung function and PRO measurements were also confirmed in real-world evidence studies and seen in clinical practice.

The duration of this study is based on previous severe eosinophilic asthma imaging-based studies that have shown a rapid response on VDP and some PROs, such as ^{CCI} at 28-days post-benralizumab, with changes detected as early as 14 days, and pronounced effects on patients with SEA and mucus plugs (McIntosh et al., 2020; McIntosh et

al., 2021; Oguma et al., 2021) following treatment with benralizumab every 4 weeks.

Based on the observations from the imaging studies, further analyses were conducted on the results from the phase 3 SIROCCO and CALIMA studies on a subgroup of participants with a similar baseline profile for age, baseline eosinophilic levels, ICS dose and pre-BD FVC, to those who will be included in the current study. The results show improvements in change from baseline in FEV_1 as early as week 8 following treatment with benralizumab 30 mg every 4 weeks compared with the placebo arm (data on file). These observations provide support for assessing outcomes in patients treated with benralizumab for a shorter duration, while ongoing trials like the CHINOOK study with a study duration of one year, will take measurements as early as 8 weeks and will be repeated at week 48.

A 13 (± 1) week study duration was selected for this study to evaluate outcomes under treatment based on the above. Further, it is also to ensure the evaluation occurs at the middle time point between the third and fourth dose of benralizumab 30 mg to increase the likelihood that participants have optimal serum concentrations during evaluation of the final measurements for the study.

Patient-reported Outcomes (PROs)

The benefits shown on other PROs at 28-days post-benralizumab (McIntosh et al., 2020; McIntosh et al., 2021; Oguma et al., 2021) also suggest the possible value of exploring the relationship with CCI CCI - a new tool, and potentially understand how it could correlate with the airway dynamic measurements. The inclusion of other fit-for-purpose PROs^{CCI}

Change in ^{CCI} following benralizumab treatment was studied in phase 3 asthma exacerbation studies, SIROCCO (Bleecker et al., 2016) and CALIMA (FitzGerald et al., 2016), the OCS reduction study, ZONDA (Nair et al., 2017), long-term extension trial, BORA (Fitzgerald et al., 2019), and the phase 3b ANDHI study in patients with severe uncontrolled

asthma on standard of care (Harrison et al., 2021), and will also be studied in ongoing trials like CHINOOK (NCT03953300, ClinicalTrials.Gov). In SIROCCO and CALIMA, improvements in ACQ-6 score were reported following benralizumab treatment in participants treated every 4 weeks and every 8 weeks (Bleecker et al., 2016; FitzGerald et al., 2016; Fitzgerald et al., 2019). Benralizumab also improved ACQ-6 scores at week 24 versus placebo, with differences observed within weeks 1 to 4 of treatment in the ANDHI study – notably, the first three doses of benralizumab were given 4 weeks apart followed by dosing every 8 weeks (Harrison et al., 2021). Changes in ^{COL} score was also studied in the ANDHI trial where 24 weeks of benralizumab treatment provided clinically meaningful and statistically significant improvements in ^{COL} total score versus placebo (Harrison et al., 2021). The inclusion of ^{COL} will also thus allow the outcomes from the current study to be put into context from previous PRO-related findings following benralizumab treatment, as well as explore content similarities and differences between

Age Selection

Only participants ≥ 18 years old will be eligible to participate in the study as there is currently no data are available for children aged 6 to 11 years old with the treatment of benralizumab, and while data is available in adolescents aged 12 to less than 18 years old permitting use of benralizumab in this patient group by the US FDA in the United States, the EMA made no recommendation on a posology. The current study will enroll participants from the US and EU. Therefore, an older age limit has been placed to allow only participants ≥ 18 years old.

There are no overall differences in safety or effectiveness observed between geriatric patients and younger patients, and other reported clinical experience has not identified differences in responses between the elderly and younger patients. However, participants older than 70 years will not be allowed to participate.

